### **7.2. Treatment administration**

It will be considered as cycle administered when the patient receives at least one treatment dose. Number of cycles administered will be described as continuous variable.

The following data will be described for each drug (palbociclib and binimetinib):

- Treatment interruption (Yes, No): If affirmative:
  - Number and percentage of patients by the no. interruptions (Categorical).
  - Reason for interruption (Categorical).
  - Total number of cycles interrupted and percentage regarding total cycles (Categorical).
- Dose reductions (Yes, No): If affirmative:
  - Number and percentage of patients by the no. dose reduction (Categorical).
  - Reason for reduction (Categorical).

The exposure treatment time will be defined as the elapsed time, in months, between the date of first administered dose of study treatment (binimetinib or palbociclib) and the end of treatment date. For patients with treatment ongoing or without end of treatment date, the last administration date of any drug will be considered.

### 7.3. Dose intensity

Dose intensity will be defined as the total of each study drug received by the patient with respect to the exposure treatment time. The dose intensity will be described as mg/week.

The relative dose intensity will be defined as the total dose of each drug received by the patient in relation to the theoretical total dose that patient should had received per protocol.

The dose intensity and relative dose intensity will be evaluated as continuous variables.

## 8. EFFICACY ASSESSMENT

### 8.1. Efficacy Assessment; general considerations

Efficacy assessment will be performed for efficacy population defined in [section 5.1](#).

Time-to-event variables will be analyzed according to the Kaplan-Meier method. Kaplan-Meier survival curves, median, 95% CI, number of events and censored and number of patients at risk will be presented.

The follow-up time is defined as the elapsed time, in months, between the date of first administered dose of study treatment (binimetinib or palbociclib) and the end of study date. For patients without end of study, the last follow-up date will be taken into account.

The *swimmer pool plot* will be provided displaying the follow-up time, the treatment exposure time and the moment of progression disease.

### 8.2. Primary efficacy endpoint. PFS

Progression-free survival (PFS) is defined as the elapsed time, in months, between the start of treatment until the documentation of disease progression (radiological RECIST v1.1 or clinical) or death due to any cause, whichever occurs first. For subjects who are alive and not present disease progression at the time of data cut-off for analysis, PFS will be censored at the last tumor assessment date, if no one tumor assessment date is available PFS will be censored at start of treatment date.

PFS will be analyzed according to the Kaplan-Meier method. Kaplan-Meier survival curves and the median estimation will be reported, along with associated 95% CI. In order to response to primary end point, PFS rate at 3 month will be estimated and the 95% CI will be reported. In addition, PFS rate at 1 year with 95% CI will be calculated.

In addition, PFS will be evaluated by mutation ERK and CDK4/6.

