## 10. STUDY SCHEDULE

Procedure	Screening (-28 to -1)	Cycle 1 and 2 (± 2 days)				Cycle 3+ (± 2 days)		EOT / Early withdrawal	Safety FU visit
		D1	D8	D15	D22	D1	D15		
Informed consent	X								
Demographic data	X								
Selection criteria	X								
Medical history	X								
Physical exam^2	X	X	X	X	X	X	X	X	X
Ophthalmological examination	X	X	X 	X	X 	X		X	X
Weight	X	X	X	X	X	X	X	X	X
Height	X								
ECOG PS	X	X				X		X	X
Vital signs	X	X	X	X	X	X	X	X	X
12-Lead ECG (qTC)	X					If clinically indicated			
LVEF (ECHO/MUGA)	X	X				X 		X	X
Hematology	X	X	X	X	X	X	X	X	X
Biochemistry	X	X	X	X	X	X	X	X	X
TSH, fT3 y fT4	X	X				X		X	X
Urinalysis	X	X				X		X	X
Coagulation	X	X				X		X	X
Serology	X					If clinically indicated			
Serum pregnancy test	X	X				X		X	X
Archival and fresh tumor biopsy	X								
Blood sample (correlative studies)		X						X	
Tumor sample (correlative studies)								X	
Tumor evaluation (PET-CT/CT/MRI)	X	X 				X 		X	
Binimetinib administration		X	X	X	X	X	X		
Palbociclib administration		X	X	X	X	X	X		
Adverse events						X			
Concomitant medications	X 	X	X	X	X	X	X	X	X

1. Medical history, including prior treatments for BC.

CONFIDENTIAL

2. A complete physical exam will be carried out during the screening visit and thereafter targeting symptoms in subsequent study visits.
3. Only cycle 1.
4. Vital Signs: pulse, blood pressure and temperature.
5. ECHO/MUGA will be performed before start binimetinib treatment, 1 month after the start of treatment and every 3 months thereafter.
6. Hematology include absolute red blood cell count (RBC), hemoglobin, hematocrit, platelet count, white blood cell count (WBC), with differential (neutrophils, lymphocytes, monocytes, eosinophils, basophils). Hematology will be performed in the 14 days previous to start study treatment.

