### 12.4. Analysis of Primary Objective

Progression free survival (PFS) is defined as the time from the date of start treatment until objective tumor progression or death from any reason. Patients who have not progressed or died at the time of analysis will be censored at the time of the latest date of assessment from their last evaluable RECIST 1.1 assessment. PFS will be analysed according to the Kaplan-Meier method. Kaplan-Meier survival curves and median will be reported, along with associated 95% CI.

Three months PFS and the corresponding 95% CI will be provided.

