### 8.3. Secondary efficacy endpoints

- **Overall response rate (ORR)** per RECIST v1.1 as assessed by investigator. ORR is defined as the proportion of patients with an overall response of complete or partial response, as per local investigator's assessment and according to Response Evaluation Criteria in Solid Tumours (RECIST) version 1.1 criteria. The table below provides a summary of the overall response calculation.

Target lesions	Non-target lesions	New lesions	Overall response
CR	CR	No	CR
CR	Incomplete response/SD	No	PR
CR	Not-evaluated	No	PR
PR	Non-PD or not all evaluated	No	PR
SD	Non-PD or not all evaluated	No	SD
Not all evaluated	Non-PD	No	Not evaluable
PD	Any	Yes or No	PD
Any	PD	Yes or No	PD
Any	Any	Yes	PD

Counts and percentages of ORR will be reported, along with associated 95% confidence interval (CI).

In addition, the response rate and ORR will be provided by mutation ERK and/or CDK4/6.

A *waterfall plot* will be provided with the percentual change of tumoral change between baseline evaluation and the patient's evaluation with the best response tumor assessment. Additionally, a spider plot with the percent change of tumoral size respect baseline evaluation in each patient's evaluation performed will be provided.

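### SAP 8.2 censors PFS at the last tumour assessment without the protocol's evaluability condition, which can raise, but never lower, the primary 3-month PFS

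*SAP*

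**What the plan says.** The two documents give different censoring dates for the primary endpoint.

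- Protocol 12.4: a patient without an event "will be censored at the time of the latest date of assessment from their last evaluable RECIST 1.1 assessment".
- SAP 8.2, for patients alive and progression-free at cut-off: "PFS will be censored at the last tumor assessment date, if no one tumor assessment date is available PFS will be censored at start of" (that is, of treatment). The second clause is the fallback.

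SAP 8.3 foresees scans that cannot be read. One row of its overall-response table (target lesions, non-target lesions, new lesions, overall response) is "Not all evaluated Non-PD No Not evaluable". Nothing in the SAP says whether such a visit counts as a tumour assessment for PFS. The SAP lists protocol version 3.0 as current and, in the text supplied, neither flags nor justifies a changed censoring rule.

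The schedule in protocol section 10 has a row "Tumor evaluation (PET-CT/CT/MRI") with a mark at screening. Its footnote asks for scans every 8 weeks until confirmed progression. The primary result is the Kaplan-Meier PFS rate at 3 months with a 95% CI (SAP 8.2), in about 25 patients.

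**The concern.** A programmer who follows SAP 8.2 to the letter may use the date of a scan that gave no usable information on tumour status. Between her last evaluable scan and that date, the patient stays in the risk set as event-free while other patients' progressions are counted. Under the protocol rule she would already have left.

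Such a patient can plausibly occur. She stops for toxicity and has the end-of-treatment scan required by protocol 10.3, but not all of her lesions are assessed. She may then have no later scan, because the follow-up visits in protocol 10.4 list no tumour evaluation, even though the schedule footnote asks for scans until confirmed progression. She remains in the efficacy population, which requires one dose and one later evaluation visit, not an evaluable scan.

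At stake is an undeclared departure from the protocol on the primary endpoint of a small single-arm trial. Its only possible effect favours the treatment, and the result will be read against the 25% and 50% figures in protocol 12.2.

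**Working it through.** **1. The plan's own figure.** Inputs from protocol 12.2: 3-month PFS of 25% against 50%, two-sided alpha 0.05, power 80%. A normal approximation for a proportion at a fixed time gives N = [(1.960 × √(0.25 × 0.75) + 0.842 × √(0.50 × 0.50)) / 0.25]² = 25.8, so 26. Power at 25 is 78.9%. The stated 25 is therefore reproduced closely. It does not depend on the censoring rule; only the estimate does.

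**2. Direction.** The Kaplan-Meier estimate is a product of factors (1 − d/n), where d is the number of events and n the number at risk at each event time. Moving a censoring date later leaves every d unchanged and leaves n equal or larger. Each factor is then equal or larger, so the SAP rule gives the same 3-month rate or a higher one. A rise needs events in other patients after the affected patient's last evaluable scan (or day 0), up to the earlier of her non-evaluable scan and month 3.

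**3. Worst case.** Suppose k of 25 patients have a non-evaluable week-8 scan as their only post-baseline scan and no event by cut-off, and d progressions are dated the same day. Kaplan-Meier counts a patient censored at a tied time as at risk.

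- SAP rule: (25 − d)/25
- Protocol rule, with the affected patients adding no time: (25 − k − d)/(25 − k)

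| d | k | SAP rule | Protocol rule | Rise (points) |
|---|---|---|---|---|
| 12 | 1 | 13/25 = 52.0% | 12/24 = 50.0% | 2.0 |
| 12 | 2 | 52.0% | 11/23 = 47.8% | 4.2 |
| 12 | 3 | 52.0% | 10/22 = 45.5% | 6.5 |
| 16 | 3 | 9/25 = 36.0% | 6/22 = 27.3% | 8.7 |

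If a fraction q of all patients follows this pattern, the expected rise is about q × (1 − S at week 8). With exponential PFS and month 3 at day 91.3, S at day 56 is 0.50^(56/91.3) = 0.654 or 0.25^(56/91.3) = 0.427. For q = 4%, 8% and 12% (assumed), the rise is then about 1.4, 2.8 and 4.2 points at a true 3-month PFS of 50%, and 2.3, 4.6 and 6.9 points at 25%. Simulation of the same pattern agrees to about 0.1 point.

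**4. Sensitivity to timing.** If the non-evaluable scan falls one day before the first event, the rise is zero. If the patient has an evaluable week-8 scan and a non-evaluable week-16 scan, only events between day 57 and day 91 matter. With 14 events at week 8 and 4 in that window, the protocol rule gives 11/25 × 6/10 = 26.4% and the SAP rule 11/25 × 7/11 = 28.0%, a rise of 1.6 points. With no events in the window, the rise is zero.

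**5. Broader assumptions.** The documents give no rate of non-evaluable scans or of loss to follow-up. Assumed: 5-20% of scans non-evaluable, 10-20% of patients lost within 26 weeks, and 25% of events being deaths or clinical progressions between scans. There were 4,000 simulated trials of 25 patients per setting. Three of the six settings at each true PFS are shown; they include the lowest and highest means.

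| True 3-month PFS | Lost | Non-evaluable | Mean rise (points) | Trials with no rise | 99th percentile (points) |
|---|---|---|---|---|---|
| 25% | 10% | 5% | 0.05 | 95.7% | 1.8 |
| 25% | 20% | 10% | 0.24 | 83.5% | 2.9 |
| 25% | 20% | 20% | 0.53 | 67.8% | 4.1 |
| 50% | 10% | 5% | 0.05 | 94.5% | 1.3 |
| 50% | 20% | 10% | 0.20 | 80.1% | 2.1 |
| 50% | 20% | 20% | 0.38 | 64.9% | 2.9 |

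The difference was never negative.

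**6. The fallback.** Every patient is due a screening scan on days −28 to −1. Read literally, a last assessment date therefore always exists, the start-of-treatment fallback is never reached, and a patient with no later scan gets a PFS time of −28 to −1 days. She is at risk at no event time, so the estimate does not change.

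**The case against.** The SAP does not say that a non-evaluable scan counts. It is silent, and its fallback makes sense only if tumour assessment means an assessment on treatment, so a sensible programmer might also exclude unusable scans. A reader might infer that the SAP treats a non-evaluable scan as proof of no progression. The text does not support that; it is the literal consequence of an unqualified phrase. What stands is that the protocol has the qualifier, the SAP lacks it, and nothing settles which applies.

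Several conditions must also coincide. The rule reaches only patients alive and progression-free at cut-off, and under SAP 8.2 death and clinical progression are events. Scans are due until confirmed progression, so a non-evaluable scan will often be followed by a usable one. A scan done on stopping for toxicity need not share a date with other patients' week-8 progressions. This stands, and it is why the worst-case figures are not the expected effect.

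The shift is small beside the sampling error: at 25 patients and 50%, a simple binomial 95% interval is ± 1.96 × √(0.25/25), about ± 20 points. This bears on priority. It does not remove a conflict whose only possible effect is upward.

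Finally, protocol 12.4 does not say post-baseline either and has no start-of-treatment fallback, so the baseline gap is not peculiar to the SAP. That is right, and the negative-time issue is only a tidy-up.

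**Conclusion.** The point holds as a conflict between protocol and SAP on the primary endpoint, with a known direction and a usually small size. Under the broad assumptions the mean rise is about 0.05 to 0.5 points, with none in most trials. The 2.0 to 8.7 points in the worked examples need one to three patients whose only post-baseline scan is non-evaluable and tied with the week-8 events, with no later scan and no event by cut-off. All of these rates are assumptions.

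Three stronger inferences are not supported.

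- That the SAP rule raises the result: it can, but only if such patients occur and other patients' events fall in the relevant interval.
- That a non-evaluable week-8 scan makes the patient progression-free at 3 months: it credits her only to week 8. Only a scan at or after about day 91, such as week 16, carries her past month 3.
- That crossing 50% would reverse a formal decision: in the illustration with 12 events, two affected patients do move the estimate from 47.8% to 52.0%. However, protocol 12.2 uses 50% as a design assumption for accepting efficacy, and neither protocol 12.4 nor SAP 8.2 sets a test or cut-off for the estimate.

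**What to change.** Before database lock, replace the censoring rule in SAP 8.2 with wording such as:

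*Patients alive without progression at data cut-off are censored at the date of the last evaluable post-baseline RECIST 1.1 assessment (any evaluable overall response other than PD, including non-PD in patients with non-target disease only; Not evaluable assessments do not count). If there is none, PFS is censored at the start of treatment.*

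This brings back the protocol's evaluability condition. Adding post-baseline clarifies the protocol rather than merely restoring it; it makes the existing fallback reachable and avoids negative times, without changing the estimate. The definition should not be limited to CR, PR or SD. Inclusion criterion 10 asks only for evaluable disease, and the SAP 8.3 table has no row for patients without target lesions, so such a limit could discard their valid non-PD scans.

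The cost is one sentence and a filter on the overall response, with an explicit rule for patients who have non-target disease only. A few patients will be censored earlier, so the confidence interval is slightly wider and the 3-month estimate may be slightly lower.

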### 8.3. Secondary efficacy endpoints

- **Overall response rate (ORR)** per RECIST v1.1 as assessed by investigator. ORR is defined as the proportion of patients with an overall response of complete or partial response, as per local investigator's assessment and according to Response Evaluation Criteria in Solid Tumours (RECIST) version 1.1 criteria. The table below provides a summary of the overall response calculation.

Target lesions	Non-target lesions	New lesions	Overall response
CR	CR	No	CR
CR	Incomplete response/SD	No	PR
CR	Not-evaluated	No	PR
PR	Non-PD or not all evaluated	No	PR
SD	Non-PD or not all evaluated	No	SD
Not all evaluated	Non-PD	No	Not evaluable
PD	Any	Yes or No	PD
Any	PD	Yes or No	PD
Any	Any	Yes	PD

Counts and percentages of ORR will be reported, along with associated 95% confidence interval (CI).

In addition, the response rate and ORR will be provided by mutation ERK and/or CDK4/6.

A *waterfall plot* will be provided with the percentual change of tumoral change between baseline evaluation and the patient's evaluation with the best response tumor assessment. Additionally, a spider plot with the percent change of tumoral size respect baseline evaluation in each patient's evaluation performed will be provided.

## 9. SAFETY ASSESSMENT

### 9.1. Safety Assessment; general considerations

The assessment will be performed for safety population defined in [section 5.1](#). Adverse events will be evaluated according to NCI CTCAE vs 5 criteria. Adverse events will be coded by the latest available version of MedDRA dictionary. AEs will be evaluated with the MedDRA code by system organ class (SOC) and preferred term (PT).

The analysis will be performed with the information completed into the adverse event eCRF section.

The analysis of adverse events will be performed per patient, for that the maximum grade for each adverse event completed of each patient will be calculated.

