## **8. WITHDRAWAL CRITERIA**

### **8.1. Reasons for Withdrawal**

Patients have the right to voluntarily withdraw from the study at any time for any reason. In addition, the investigator has the right to withdraw a patient from the study at any time.

Every effort should be made to obtain information on patients who withdraw from the study. The primary reason for withdrawal from the study should be documented on the appropriate eCRF.

Reasons for withdrawal from the study may include but are not limited to the following:

- Unacceptable toxicity.
- If, in the investigator's opinion, continuation of study would be harmful to the patient's well-being.
- Any toxicity requiring dose reduction below 30 mg/BID of binimetinib or 75 mg daily of palbociclib.
- Any toxicity requiring dose interruption longer than 28 days to resolve to Grade 1 or better.
- Any other potential adverse reaction deemed sufficiently serious to warrant discontinuation of treatment by the investigator or his designated associate(s).
- Any decrease in visual acuity, or symptomatic or asymptomatic retinal disorders including retinal detachment / retinal pigment epithelial detachment / serous retinopathy / **retinal vein occlusion** classified analog to CTCAE v.5 as Grade 2 or higher. Based on the individual benefit risk assessment and after discussion with the sponsor, patient may interrupt treatment until recovery to at least Grade 1 and then treatment may be resumed at one dose level below.
- Grade 4 non-hematological toxicity (laboratory abnormalities of any grade will not be considered toxicity unless deemed clinically significant by the investigator).
- Any AE that meets criteria for discontinuation.

- Subject noncompliance that warrants withdrawal in the opinion of the investigator or sponsor.
- Initiation of alternative anticancer therapy including another investigational agent.
- Confirmation of PD and investigator determination that the subject is no longer benefiting from treatment with study treatment.

If the administration of any of the study drugs has to be stopped, the site principal investigator will consult with the sponsor to withdraw the patient from the study (depending on the duration of treatment, if she has benefit, if the benefit is attributed to the suspended drug, etc.).

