7. Alkaline phosphatase, aspartate aminotransferase (AST), alanine aminotransferase (ALT), $\gamma$ -glutamyltransferase (GGT), total bilirubin; blood urea/blood urea nitrogen (BUN), creatinine: creatinine clearance; glucose, albumin, cholesterol, triglyceride, phosphorus, lactate dehydrogenase (LDH), total protein, uric acid, creatinine phosphokinase (CPK); Sodium, potassium, calcium, magnesium, chloride, bicarbonate (HCO3). Biochemistry will be performed in the 14 days previous to start study treatment.
8. Free T3 and free T4 will only be measured if TSH is abnormal. They should also be measured if there is clinical suspicion of an adverse event related to the endocrine system. In the 14 days previous to start study treatment.
9. Urinalysis: bilirubin, blood, glucose, ketones, PH, protein specific gravity, colour and appearance. Dipstick test every cycle. Additional analyses will be done at investigator criteria in case of abnormal results. Urinalysis will be performed in the 14 days previous to start study treatment.
10. Coagulation tests: prothrombin time, APTT and INR. In the 14 days previous to start study treatment.
11. Serology: hepatitis B surface antigen, hepatitis C antibody, HIV antibody. In the 14 days previous to start study treatment and if clinically indicated thereafter.
12. Serum pregnancy test only pre-menopausal female subjects of childbearing potential. At study entry, every 4 weeks during the study treatment and at the end of study treatment.
13. All formalin-fixed, paraffin-embedded (FFPE) tissue samples block and one hematoxylin and eosin (H&E) stained tumor slide, both obtained in the 15 days before patient inclusion in the study, will be sent to CNIO in order to determine positivity of ERK and/or CDK4/6, preferably obtained after last treatment or the most recent sample as possible (from metastatic site or first diagnosis according to sample availability).
14. Tumor evaluation will be performed every 8 weeks until confirmed PD.
15. 21 days-on/7 days-off.
16. This applies to all non-serious AEs and SAEs that occur at any time during the administration of the study drug and up to 30 days after end of treatment.
17. Concurrent medications administered within the 28 days preceding day 1.
18. Blood sample: two CPT tubes of 7 ml will be obtained at baseline visit before treatment administration, at C2D1 and at disease progression (a 2 weeks window is allowed from confirmation of disease progression).

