## **10.2. Study treatment visits**

Study patients will be evaluated weekly during the first 2 months and every 2 weeks thereafter.

The following procedures will be performed during study treatment:

- Tumor evaluation: PET-CT, CT and/or MRI (every 8 weeks)
- Physical examination: will be performed at screening and thereafter targeting symptoms in subsequent study visits
- Ophthalmological examination: Ask patient for changes in vision at every visit. If change in vision is reported, an ophthalmological examination must be performed preferably within 3 days. Ophthalmologic examination will be performed weekly during first cycle, biweekly during second cycle and every 4 weeks thereafter. Particularly for patients who experience any decrease in visual acuity, or symptomatic or asymptomatic retinal disorders including retinal detachment / RPED / serous retinopathy / retinal vein occlusion (Grade 1 analog to CTCAE v.5) have to undergo ophthalmologic examinations on day 1 of every cycle.
- Weight: in all study visits

- Vital Signs: pulse, blood pressure and temperature; every week during first two cycles, and days 1 and 15 of each cycle thereafter
- ECOG performance status (day 1 of every cycle)
- 12-lead ECG: if clinically indicated
- ECHO/MUGA: before start binimetinib treatment, 4 weeks after the start of treatment and every 12 weeks thereafter.
- Hematology: every week during first two cycles, and days 1 and 15 of each cycle thereafter
- Biochemistry: every week during first two cycles, and days 1 and 15 of each cycle thereafter. Safety laboratory tests can be collected up to 2 days prior to drug administration.
- TSH, fT3 y fT4: day 1 of every cycle. Free T3 and free T4 will only be measured if TSH is abnormal.
- Coagulation: day 1 of every cycle
- Urinalysis: day 1 of every cycle
- Serologies: if clinically indicated
- Pregnancy Testing: every 4 weeks (day 1 of each cycle). Pre-menopausal women of childbearing potential only
- Adverse events: in all study visits
- Concomitant medications: in all study visits
- Blood sample: two CPT tubes of 7 ml will be obtained before treatment administration at D1C1 and D1C2.

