### **11.1. Definitions**

#### **11.1.1. Adverse event (AE)**

An AE is any undesired experience that occurs in a patient participating in clinical research that is associated in time with the use of a medicinal product, whether or not it is considered to be related to the investigational products. Therefore, an adverse event can be any unintentional unfavorable sign (including an anomalous laboratory result), symptom or disease that is associated in time with the use of a medicinal product, whether or not it is considered to be related to the product. Pre-existing diseases that worsen during the study shall be notified as Adverse Events.

AEs include pre- or post-treatment events that occur as a result of study procedures (e.g. invasive procedures or modification of the patient's previous medication).

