### **11.1.3. Additional considerations**

Alterations in laboratory parameters (hematology, biochemistry or urine analysis), as well as anomalous results of other studies (such as ECGs, radiology, measurements of vital constants), including those that deteriorate in relation to baseline, should be recorded as AEs or SAEs if, in the medical and scientific opinion of the investigator, they are clinically relevant.

On the contrary, clinically significant alterations in safety parameters that are associated with the study disease are not characterized as AEs or SAEs unless the investigator thinks that they are more serious than would be expected considering the state of the patient.

Lack of efficacy (i.e., disease progression) is a disease-related event and should not be classified as a SAE. Death as a result of disease progression is also excluded from the definition of SAEs.

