#### **Muscle Enzyme/Protein Changes and Myopathy/Rhabdomyolysis-Related AESIs**

Muscle enzyme/protein changes were frequently observed, although Grade 3/4 events were less common in patients. All patients with an event in the muscle enzyme/protein changes grouping had at least 1 event reported under the PT of blood CK increased. No other muscle enzyme/protein changes by PT were reported in  $> 5.0\%$  of patients in either population.

Events in the myopathy grouping were reported; few patients had a Grade 3/4 event. The myopathy event reported in  $> 5.0\%$  of patients in either population by PT was myalgia.

Events in the rhabdomyolysis grouping were uncommon.

Symptomatic muscle-related AEs reported in the myopathy and rhabdomyolysis groupings that occurred within 15 days before to 30 days after the worst laboratory CK elevation were analyzed. Around 6% of patients with a worst post-baseline laboratory CK value  $\geq$  Grade 1 had at least one symptomatic muscle-related AE reported.

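### Safety tables come from the adverse event form alone, so rates of laboratory-defined toxicity depend on investigator judgement, and no summary of the measured laboratory or LVEF results is specified

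*SAP*

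**What the plan says.** SAP 9.1 names a single data source for the safety assessment: "The analysis will be performed with the information completed into the adverse event eCRF section". SAP 9.2 to 9.5 then define counts and listings of adverse events, adverse reactions, SAEs and AESIs. Protocol 12.5.2 plans the same kind of output, AE and toxicity frequencies by grade.

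Protocol 11.1.1 counts as an AE "any unintentional unfavorable sign (including an anomalous laboratory result". Protocol 11.1.3 then narrows this. Laboratory changes and other abnormal test results "should be recorded as AEs or SAEs if, in the medical and scientific opinion of the investigator, they are clinically relevant". Changes associated with the study disease, even clinically significant ones, are left out unless the investigator thinks them more serious than the patient's condition would lead one to expect.

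The underlying measurements are frequent. Protocol 10.2 has "Hematology: every week during first two cycles, and days 1 and 15 of each cycle thereafter" and "Biochemistry: every week during first two cycles, and days 1 and 15 of each cycle thereafter". The biochemistry panel in the section 10 schedule includes CPK, AST, ALT and bilirubin. LVEF is measured before treatment, at 4 weeks and every 12 weeks thereafter.

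Two other SAP statements bear on the point. Section 2 says that the SAP defines the tables, figures and listings of the study. Section 4 commits in general terms to listing and tabulating all available efficacy and safety data.

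**The concern.** Safety of the combination is a secondary objective, and much of the toxicity the protocol expects is defined by a laboratory value. Of the seven common Grade 3 or higher palbociclib reactions in Protocol 5.1.2.1, five are laboratory findings (neutropenia, leukopenia, anaemia, AST and ALT increase). For binimetinib, Protocol 5.1.3.5.1 singles out CK increase as the frequent event that is often Grade 3/4, and Protocol 5.1.3.6 describes CK elevations as mostly without symptoms.

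For such events the measured value determines the grade in most cases. The plan instead counts them only after an investigator at one of 8 sites has decided that the value is relevant and is not explained by the disease. A reader of the final tables could not tell a low rate of Grade 3/4 abnormalities from a low rate of recording them.

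**Working it through.** The plan states no figure on this point, so there is nothing to reproduce. The check sets the provisions side by side and then shows how sensitive a rate is in a trial of this size.

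**1. Is a laboratory or LVEF summary specified?** SAP 9.2 to 9.5 contain none. SAP 6.2 omits haematology and biochemistry at baseline and describes ECHO/MUGA only as done or not done and normal or abnormal. SAP section 4 could be read to cover these data, but it fixes no parameter, grading or comparison with baseline, and 9.1 restricts the safety analysis to the AE form. The two sentences do not fit together.

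**2. Which abnormalities can go uncounted?** Many have a second trace. Where a drug is withheld or reduced, SAP 7.2 tabulates the reason for the interruption or reduction. Two groups lack that trace or are filtered twice:
- Abnormalities where the protocol keeps the dose unchanged: asymptomatic Grade 3 CK (Protocol 9.3.2) and Grade 3 haematological toxicity on Day 15 of the first two cycles (Protocol 9.3.1).
- Changes that can be attributed to the disease under Protocol 11.1.3. A transaminase rise in a patient with liver metastases, eligible at up to 5 times ULN, is an example.

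The AESI section does not close the gap. Its listing also depends on the AE form, and the counts in SAP 9.5 are worded for serious events.

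**3. How sensitive is a rate?** With N = 25, one unrecorded patient changes a reported percentage by 1/25 = 4 percentage points.

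For a wider illustration, the expected recorded count is N × p × c. Here p is the proportion of patients with a Grade 3/4 CK value and c is the share of those entered on the AE form. The documents give no value for c, so it is an assumption. For p, the 21% and 29% in Protocol 5.1.3.5.1 (single-agent binimetinib) are borrowed. They are AE reports, so treating them as laboratory rates is also an assumption.

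| c (assumed) | p = 21% | p = 29% |
|---|---|---|
| 100% | 25 × 0.21 = 5.25 | 25 × 0.29 = 7.25 |
| 75% | 3.94 | 5.44 |
| 50% | 2.63 | 3.63 |
| 25% | 1.31 | 1.81 |

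The table shows only that the reported count follows c in direct proportion. It does not say what c will be.

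**The case against.** The strongest reply is that investigators do record these events. The 21% and 29% CK figures appear in the protocol as reported AEs; in the phase 3 ovarian study the 29% is 66 patients with an AE of at least Grade 3. CK increase of any grade was reported in 53% of binimetinib patients in that study and in 81.0% in the Japanese phase 1 study. An event that is mostly asymptomatic was therefore entered often. The AE definition admits abnormal laboratory results, grades that lead to withholding a drug are hard to call irrelevant, and SAP 7.2 gives a second view of those. The SAP also implements the endpoint as the protocol states it, the number of patients with each AE by grade, and no document promises shift tables. All of this stands. It means that undercounting is a risk and not a finding. It does not make the recording complete, and it does not reach the events where dosing continues.

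A reader might infer more than the documents support, in four ways.
- That laboratory results will never be summarised. SAP section 4 promises otherwise in general terms; the accurate statement is that no such table is specified.
- That only 0 or 1 Grade 3/4 CK cases would be recorded instead of 5 to 7, by applying the figure that begins "Around 6% of patients with a worst post-baseline laboratory CK value". That 6% is the share of patients with CK elevation of Grade 1 or higher who also had a symptomatic muscle AE. It is not a recording rate, and Protocol 11.1.3 does not equate relevance with symptoms.
- That Protocol 8.1 sets a recording rule where it says "laboratory abnormalities of any grade will not be considered toxicity unless deemed clinically significant by the investigator". The parenthesis qualifies one withdrawal criterion, Grade 4 non-haematological toxicity, and does not govern entry on the AE form.
- That the bias is downward and varies by site. Variation between sites is possible, but no figure in the documents shows any.

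**Conclusion.** The point holds as a gap in specification. The only safety source named in SAP section 9 is a form that laboratory findings enter by investigator judgement, while the measured values that would give the grade directly have no defined table. The main exposure is abnormalities where the dose is maintained and changes that can be put down to the disease.

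The size is unknown and may be zero. It rests on the share of laboratory Grade 3/4 events entered as AEs, which the documents do not give and which the earlier binimetinib studies cannot supply. What can be stated is the sensitivity: 4 percentage points for each unrecorded patient. The primary endpoint and the sample size are unaffected. The change should be made because it removes the dependence at little cost, not because undercounting has been shown.

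**What to change.** Before database lock, amend SAP section 9 as follows, for the safety population:
- Tabulate worst post-baseline CTCAE v5 grade and the shift from baseline, computed from the recorded values, for neutrophils, platelets, haemoglobin, AST, ALT, bilirubin and CPK. State which pre-treatment value is the baseline.
- Show these tables beside the AE-form tables, which remain the protocol's stated endpoint.
- Add worst LVEF and change from baseline if the eCRF holds LVEF as a number. SAP 6.2 describes only a normal/abnormal result at baseline, so this must be checked first.
- Reconcile SAP section 4 with 9.1, so that 9.1 names the laboratory data as a second source for the safety analysis.

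The cost is a few more tables and SAP wording, provided that the numeric laboratory values are in the eCRF. Protocol 13.5 calls in general terms for source information to be entered there but lists no fields, so this too needs confirming. The downside is that Grade 3/4 laboratory rates may look less favourable than the AE tables alone would show.
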